Psychiatric comorbidities are common in headache (Breslau et al., 2003), and comorbid psychopathology has been linked to alterations in headache evolution and treatment response (Antonaci et al., 2011). Ruff et al. (2012) estimate that more than 80% of Veterans diagnosed with mTBI and PTHA also have PTSD. Although comorbid headache and PTSD may alter the effectiveness of interventions, there is some evidence to suggest that addressing PTSD directly can ameliorate health symptoms like headache (Shipherd et al., 2013). There are no studies, however, examining the influence of PTSD comorbidity in posttraumatic headache in a military population, so the gaps in PTHA intervention extend beyond targeted non-medication interventions to PTSD treatments that address PTHA through alterations in PTSD symptom severity. In fact, an ongoing PTSD trial overseen by [name], has revealed subjective reports of headache improvement among military service members who are successfully treated for PTSD. We have chosen to add a treatment arm to this study design in which participants with PTHA and comorbid PTSD or PTS symptoms will be treated with a gold-standard, manualized PTSD intervention (Cognitive Processing Therapy; CPT-C). Both CPT-C and the manualized headache intervention rely upon cognitive behavioral mechanisms that overlap and may produce relief for both disorders.

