- have been diagnosed or report symptoms consistent with chronic (> 3 months) posttraumatic headache attributed to a traumatic injury. We are focusing on chronic PTHA due to the very low likelihood of headache remission after 3 months, the disability associated with chronic PTHA, and the high prevalence of chronic versus acute PTHA in this population. A positive PTHA diagnosis will be indicated for individuals with de novo headache onset after a concussion or exacerbation of pre-existing headache symptoms (increased frequency, duration, or intensity), which is consistent with the existing ICHD-IV diagnostic criteria for PTHA. PTHA inclusion will be based on a consultation with one of our PRC/Polytrauma System of Care (PSC) co-PIs/overall study PI if symptoms consistent with chronic PTHA are reported, but the diagnosis is not already documented in the participant's medical record.
- If taking headache medication, participant must agree to work with their prescriber to remain on stable doses of any prescribed headache medications for the duration of the intervention and through the follow-ups as much as possible and as medically indicated..
- Participants must also report on the Clinician Administered PTSD Scale (CAPS-5) an exposure to a traumatic event (Criterion A) and at least one intrusion symptom (Criterion B). There is some evidence suggesting 40% comorbidity between PTSD and new onset headache, so it is reasonable to assume that at least half of all PTHA participants recruited for this study will have PTHA and comorbid PTS symptoms. The inclusion of PTS symptoms in this sample is vital based on reports indicating that PTS symptoms and PTSD actually increase vulnerability to PTHA and chronic headache in military populations.

Exclusion Criteria:

- Participant has had a recent and significant change in the nature of headache symptoms over the last 6 weeks prior to screening (as determined by the investigators).
- Participants currently in CPT or prolonged exposure for PTSD.
- Participant has medication overuse headache as guided by the Structured Diagnostic Headache Interview-Revised (Brief Version; SDIH-R) and clinical judgment.
- Participant is unable to read or speak English at a 6th grade level.
- Participant has had a psychiatric hospitalization in the last 6 months.
- Participant is pregnant or plans to become pregnant during the trial (due to concerns about pregnancy-induced headache that may obscure findings)

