Advanced Data Center (ADC) has 24x7 onsite security, card key, biometric access controls and video surveillance. University of Texas Health Science Center at San Antonio (UTHSCSA) ADC facility also maintains Gen 2 firewall devices to protect and prohibit any unauthorized access to UTHSCSA data. All UTHSCSA network devices are monitored by state of the art monitoring applications that include configuration audit, management, and availability 24x7.

Statistical Consideration

6.3.1 Sample Size Estimation.

This study will consent approximately 438 study participants with the goal of having 192 participants randomized for analysis.

6.3.2 Primary (i.e., primary outcome variables) and secondary endpoints.

The primary outcomes are headache symptoms and PTSD symptoms.

6.3.3 Data analysis.

Treatment groups will be compared on baseline variables. Dropout during treatment resulting in lack of outcome data can bias analyses. If attrition can be successfully modeled with logistic regression on the basis of baseline characteristics, and particularly if there is evidence of differential attrition, strategies such as inverse probability weighting can supplement the outcome analyses. Assuming that headache disability data (HIT-6; our primary outcome for this research) is reasonably normally distributed across the sample, treatment effects of the clinical interventions (CCBT and CPT-C) over the Treatment as Usual- Control condition will be analyzed using a general linear mixed (GLM) model with baseline scores used as a covariate. Unlike ANOVA, mixed effects models permit heterogeneity of variance in the treatment groups. If HIT-6 data are non-normal, a generalized linear model will be used (e.g., Poisson regression).

Two joint primary comparisons will be conducted comparing both active treatments to TAU. To adjust the alpha level for these joint hypotheses, we will interpret both at the alpha = 0.025 significance level. Secondary analyses will examine differences between the two active interventions as well as sensitivity analyses of the primary outcomes considering missing data, adherence to the protocol, or imbalances between the groups at baseline. Additional analyses will consider the secondary outcomes and differences between the groups at other time points.

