A recent study helped to guide our determination of what constitutes a clinically meaningful change in perceived headache disability and the proposed study was powered in light of these differences. In the primary care setting, HIT-6 changes ranging from 2.5 (95% CI: -3.3 to -1.7) were perceived as "somewhat better" and changes up to 5.9 (95% CI: -7.6 to -4.1) were perceived as "much better." We considered a meaningful change as somewhere between these two global impressions and used this marker as an index of clinically significant between-group differences. Our study is powered to detect an effect size of 2.8 points between groups after controlling for baseline scores (i.e., a residualized change) and constitutes an effect that would be meaningful to most headache sufferers. Assuming an alpha level of 0.025, group sample sizes of $n = 64$ ($N = 192$), and a moderate correlation between the baseline scores and final endpoints ($r = 0.50$), we will have power = 0.80 to detect an effect size of $d = 0.52$ between both of the joint primary comparisons. In realistic terms, this will allow us to detect a change of 2.8 points on the HIT-6 between the active treatment and the controls. Changes smaller than this magnitude are unlikely to be clinically meaningful.

6.4 Confidentiality.

Confidentiality will be safeguarded through a number of Consortium controls already in place for existing studies. First, all assessments will occur in a private room. Completed hard-copy assessments will be stored in a file in a locked drawer that is located in a locked office at the VA or the UTHSCSA STRONG STAR clinic. Patient identifiers are removed from all charts and associated only with a number identifier. Data will be transcribed into the Consortium database by the study coordinator or a trained research assistant using a double-entry method. All digital research data files will be encrypted and password-protected on the UT Health Science Center's FISMA-compliant network, with files accessible only to the Consortium Data Core. All UTHSCSA STRONG STAR network connectivity is segmented with Access Control Lists and is not accessible to any other UTHSCSA network segments. The STRONG STAR data server is physically located at the Advanced Data Center (ADC) has 24x7 onsite

Randomized Clinical Trial of Cognitive-Behavior Therapy for Posttraumatic Headache

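### The primary HIT-6 model names baseline HIT-6 as its only covariate; pre-specifying baseline CAPS-5 as well would be a free, modest gain in precision

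*Combined protocol and SAP*

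**What the plan says.** Section 6.3.3 (Data analysis) states that the effects of the two therapies over TAU on HIT-6 "will be analyzed using a general linear mixed (GLM) model with baseline scores used as a covariate". The power paragraph of the same section describes the target as a residualized change and quotes a correlation of 0.50 between baseline scores and final endpoints, so the covariate is baseline HIT-6. No PTSD measure is named, and no stratified randomisation is described.

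Other parts of the document bear on that choice:

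- Section 4 says that "comorbid psychopathology has been linked to alterations in headache evolution and treatment response".
- Section 6.1.3 adds that posttraumatic stress symptoms raise vulnerability to posttraumatic and chronic headache. It sets a low entry threshold: "Participants must also report on the Clinician Administered PTSD Scale (CAPS-5) an exposure to a traumatic event (Criterion A") and at least one intrusion symptom. Severity can therefore run from a single intrusion symptom to full PTSD.
- The assessment schedule in 6.1.2 collects CAPS-5 and PCL-5 at baseline.

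Other baseline variables appear in 6.3.3 in two places. One is an optional attrition model with inverse probability weights. The other is a set of sensitivity analyses for missing data, adherence, "or imbalances between the groups at baseline". Neither names a variable.

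**The concern.** A baseline variable that predicts the outcome beyond baseline HIT-6 reduces residual variance when it is in the model, and so adds power without adding patients. The protocol itself gives reasons to expect PTSD severity to be such a variable. CAPS-5 is used for eligibility, so it should be available for every randomised participant.

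There is a second, conditional stake. If people with more severe PTSD left one arm more often than another, the completers would differ in PTSD severity between arms. A model holding only baseline HIT-6 would pass part of that difference into the treatment contrast. CAPS-5 in the model would remove the part explained by baseline PTSD severity.

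**Working it through.** **Inputs from 6.3.3.** Alpha: "we will interpret both at the alpha = 0.025 significance level". Size: "group sample sizes of $n = 64$ ($N = 192"), so 64 per arm. Power: "we will have power = 0.80 to detect an effect size of $d = 0.52$ between both of the joint primary comparisons". Baseline-endpoint correlation r = 0.50; difference 2.8 HIT-6 points. The implied SD is 2.8 / 0.52 = 5.38. Sidedness is not stated; two-sided 0.025 is used here.

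**Inputs assumed.** The share p of residual HIT-6 variance explained by baseline CAPS-5 is taken as 3-10%, a partial correlation rho = sqrt(p) of about 0.17 to 0.32. The documents give no value. A second case of 51 analysable per arm (about 20% loss) is also an assumption; the plan states no dropout rate.

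**Step 1: the plan's own figure.** Power is taken from the noncentral t distribution with 2n - 2 degrees of freedom and noncentrality (0.52 / s) x sqrt(n/2). For n = 64 the critical value is 2.269.

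- If d = 0.52 is on the raw SD, s = sqrt(1 - 0.50^2) = 0.866, the noncentrality is 3.397 and power is 0.869.
- If d = 0.52 is already on the residual SD, s = 1, the noncentrality is 2.942 and power is 0.749.

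The stated 0.80 lies between the two and matches neither. With the raw-SD reading it is reached at about 54 analysable per arm. That is a separate matter; both readings are carried forward.

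**Step 2: add CAPS-5.** Multiply s by sqrt(1 - p).

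| Reading | p = 0 | p = 3% | p = 10% |
|---|---|---|---|
| Raw SD, 64 per arm | 0.869 | 0.880 | 0.904 |
| Raw SD, 51 per arm | 0.774 | 0.788 | 0.820 |
| Residual SD, 64 per arm | 0.749 | 0.763 | 0.796 |

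The gain is 1.1 to 4.7 power points. At 64 per arm with rho = 0.2 (p = 4%) it is 1.4 points on the raw-SD reading (0.883) and 1.9 on the residual reading (0.768). With rho = 0.1 (p = 1%) it is about half a point.

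**Step 3: the dropout scenario.** Shift in the contrast = rho x residual SD x between-arm difference in mean baseline PTSD severity (in SDs) among completers. The residual SD is taken as 5.38, and higher severity is assumed to go with worse HIT-6. All dropout patterns are assumed.

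- *Therapy-arm dropout 20% below and 50% above median severity, TAU dropout unrelated to severity.* The half-normal mean is 0.798, so completers differ by 0.798 x (0.50 - 0.80) / (0.50 + 0.80) = -0.184 SD. With rho = 0.3 the shift is 0.3 x 5.38 x 0.184 = 0.30 points in favour of therapy. It is 0.26 if 5.38 is the raw SD (residual SD 4.66).
- *Logistic dropout, 30% in therapy with odds ratio 2 per SD, 15% in TAU unrelated to severity.* Completers differ by 0.190 SD; the shift is 0.10 to 0.41 points for rho 0.1 to 0.4.
- *Therapy-arm dropout raised to 40%, the rest unchanged.* The difference is 0.251 SD; the shift is 0.13 to 0.54.
- *Odds ratio 1.5 in both arms, dropout 30% and 15%.* The difference is 0.058 SD; the shift is 0.03 to 0.12.
- *The same odds ratio and the same rate in both arms.* The shift is zero.

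For scale, the standard error of the contrast with all 64 per arm is 5.38 x sqrt(2/64) = 0.95 points, so a shift of 0.30 is about a third of a standard error.

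**The case against.** The strongest reply is that nothing here is an error. A baseline-adjusted comparison of randomised arms is standard and valid, the plan is powered on that model, and leaving out a second covariate contradicts no part of the document. That stands.

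Some stronger readings are tempting, and the documents do not support them.

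- *That protection against PTSD-related dropout is given away.* It is not. Section 6.3.3 plans an attrition model with optional weighting and missing-data sensitivity analyses. Section 6.2 plans a telephone HIT-6 and PCL-5 for consenting participants who discontinue, and item 39 of the study measures is meant to examine whether data are missing at random and to support imputation. Outcome data from dropouts can also address missingness that no baseline covariate captures. What remains is that these measures are conditional, name no PTSD variable and leave the primary estimate unchanged.
- *That PTSD severity drives dropout.* No section says so. Section 3 of the argument above is a scenario; where section 4 of the protocol discusses failure to complete follow-up in medical care, it names mTBI and headache disability.
- *That covariates for the primary test will be chosen from observed imbalance.* The imbalance analysis is only a sensitivity analysis, and the primary covariate is already fixed. It does not mention PTSD.
- *That the covariate would deal with altered treatment response.* Effect modification is not addressed by a main-effect term. The relevant statements are those on headache course, and they are qualitative: none shows how much PTSD severity predicts final HIT-6 once baseline HIT-6 is known.

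The size of the gain therefore rests wholly on an assumed correlation.

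**Conclusion.** The omission is clear from the text; its size is not. The primary comparison is valid without CAPS-5. Under an assumed 3-10% of residual variance explained, the plan forgoes about 1 to 5 power points per comparison, and less if the partial correlation is below about 0.2. Under assumed arm-specific dropout related to PTSD severity, the primary estimate could shift by roughly 0.1 to 0.4 HIT-6 points, up to about 15% of the 2.8-point target (0.41 / 2.8). With other assumed patterns the shift ranges from zero to 0.54. This is a free improvement, not the repair of a flaw.

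**What to change.** In 6.3.3, replace the unspecific reference to baseline scores with a statement that the primary HIT-6 model includes baseline HIT-6 and baseline CAPS-5 total severity as fixed, pre-specified covariates. Name baseline CAPS-5 among the predictors in the attrition and weighting model. The baseline-imbalance analysis may stay as a sensitivity analysis.

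The cost is one or two sentences and one degree of freedom in the primary model. It needs no new data and no more patients. The change should be made before outcome data are examined by arm.

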12. Structured Diagnostic Headache Interview-Revised (Brief Version; SDIH-R): The SDIH-R is a structured clinical interview assessing headache symptoms that conform to the ICHD-II criteria for primary and posttraumatic headache (Silberstein, 2000; Campbell, Penzien, & Wall, 2000). This interview will be administered at the baseline assessment session to further establish the participant's headache diagnosis and again at post-treatment and six-month follow-ups (to help establish the perseverance or dissolution of the PTHA diagnosis in response to treatment).
13. Daily Headache Diary (Online) (Goslin et al, 1999): Headache frequency and severity will be assessed via daily headache self-monitoring diaries. Patients will complete the assessment twice daily (during AM and PM), requiring 5 to 10 minutes per assessment. Although the descriptions of when the various forms are completed are made in reference to a typical sleep-wake cycle, it is of note that the "morning" (AM) entry simply refers to the entry that is made when a subject awakens and the "evening" (PM) entry is made at the end of their waking day (thus, the entries can easily be adapted for individuals doing shift work). They will record their headache intensity 2 times during the day using a 0 to 10 scale, with 0 representing "no headache" and 10 representing a headache that was "extremely painful—I can't do anything when I have this headache." From these diaries, 4 dependent measures will be computed for each assessed week: (a) days per week with a headache (days with headache greater than 2); (b) weekly headache frequency (total number of discrete headaches per week); (c) headache duration (total number of hours of headache per week with headache greater than 2); and (d) average peak headache intensity. The Headache Diary also tracks the occurrence of known headache triggers and medication use for headache management (prophylactic and abortive).
14. Headache Impact Test-6 (HIT-6): The HIT-6 is a 6-item measure of headache-disability considered a gold standard in headache clinical and research work. Developed in 2003 (Kosinski et al, 2003), the HIT-6 has demonstrated excellent reliability (internal consistency = 0.89; test-retest reliability = 0.80) and validity (relative validity coefficients ranging from 0.82 to 1.00). There are almost 100 published studies of headache using the HIT-6, including previous studies of PTHA (Schwedt et al, 2007).

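### The primary HIT-6 model hangs on an undefined normality check, and the only fallback named, Poisson regression, would lose much of the power at the plan's own SD if fitted with default standard errors

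*Combined protocol and SAP*

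**What the plan says.** Section 6.3.3 names HIT-6 as the primary outcome and plans a linear mixed model with the baseline score as covariate, on the assumption that HIT-6 "is reasonably normally distributed across the sample". If that assumption fails: "If HIT-6 data are non-normal, a generalized linear model will be used (e.g., Poisson regression".

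Other parts of the same section bear on this:

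- The mixed model is preferred for a stated reason: "Unlike ANOVA, mixed effects models permit heterogeneity of variance in the treatment groups".
- Each active arm is compared with TAU, and "we will interpret both at the alpha = 0.025 significance level".
- The target effect is in points and adjusted for baseline: "Our study is powered to detect an effect size of 2.8 points between groups after controlling for baseline scores". It is repeated as "this will allow us to detect a change of 2.8 points on the HIT-6 between the active treatment and the controls".
- The secondary analyses include "sensitivity analyses of the primary outcomes considering missing data, adherence to the protocol, or imbalances between the groups at baseline". The choice of distribution is not in that list.

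Item 14 of the Description of Study Measures states: "The HIT-6 is a 6-item measure of headache-disability". The documents give no HIT-6 mean, SD or range.

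**The concern.** Two things are left open in the main analysis.

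First, the switch between models has no rule. The plan does not say how far from normal is too far, whether baseline scores, follow-up scores or residuals are examined, at which visit, or whether the check is made blind to arm.

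Second, the fallback is barely specified, and its one example suits the outcome poorly. Default Poisson standard errors set the variance equal to the mean. That may be reasonable for counts of events, but nothing ties the variance of a six-item score to its mean. The test runs at its stated level only if the two happen to agree. Tying variance to mean also gives up the plan's own reason for the mixed model, that variance may differ between arms. In addition, a log-link coefficient is a ratio, whereas the effect the trial was sized for is in points.

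At stake is the chance of detecting the 2.8-point effect in the primary comparison.

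**Working it through.** **Inputs from section 6.3.3.** 64 per arm; alpha 0.025 per comparison (sidedness not stated, taken as two-sided, z = 2.241); effect 2.8 points; d = 0.52; baseline–endpoint correlation r = 0.50. **Assumption:** mean HIT-6 of 40, 50, 60 or 65.

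**The plan's own power.** The implied SD is 2.8/0.52 = 5.38. It is read as a residual SD, because the plan describes the 2.8 points as adjusted for baseline. The standard error of a difference is 5.38 × √(2/64) = 0.952, and 2.8/0.952 = 2.942. Linear-model power is Φ(2.942 − 2.241) = 0.758 (0.749 by noncentral t). The stated 0.80 is not reproduced, but that is a separate matter; 0.76 is the like-for-like comparator here. If 5.38 is the raw SD, the residual SD is 5.38 × √(1 − 0.25) = 4.66 and linear-model power is 0.876.

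**Default Poisson on the same inputs.** The ratio of the default Poisson standard error to the true one is √mean / SD. Then:

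- type I error = 2 × [1 − Φ(2.241 × ratio)]
- power = Φ(2.8/SE − 2.241 × ratio)

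Example at mean 50, SD 5.38: ratio = 7.071/5.385 = 1.313 and 2.241 × 1.313 = 2.943. Type I error is 0.003 and power is Φ(2.942 − 2.943) = 0.50. In points, the observed difference must exceed 2.241 × √50 × √(2/64) = 2.80 to be significant, against 2.241 × 0.952 = 2.13 under the linear model.

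| Assumed mean | Type I error, SD 5.38 | Power, SD 5.38 (linear 0.76) | Type I error, SD 4.66 | Power, SD 4.66 (linear 0.88) |
|---|---|---|---|---|
| 40 | 0.008 | 0.62 | 0.002 | 0.64 |
| 50 | 0.003 | 0.50 | 0.001 | 0.50 |
| 60 | 0.001 | 0.39 | 0.0002 | 0.37 |
| 65 | 0.001 | 0.34 | 0.0001 | 0.32 |

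The test is conservative whenever the mean exceeds the residual variance: 5.38² = 29.0, or 4.66² = 21.7.

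**Simulation check** (three arms of 64, r = 0.50, rounded scores, residual SD 5.38, means 50/60/65):

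- Default Poisson: power 0.52/0.40/0.34, type I error 0.0007–0.0017.
- Linear ANCOVA: power 0.74–0.75, type I error 0.026–0.028.
- Poisson with Pearson-scaled or sandwich standard errors: power 0.74–0.77, type I error 0.027–0.032.
- Skewed residuals at mean 60: linear model type I error 0.027 and power 0.75; default Poisson power 0.40.

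**Effect of choosing between models** (same setting, means 50 and 60). Taking the more favourable of linear and default Poisson left type I error unchanged (0.025 and 0.022). Taking the more favourable of linear and sandwich Poisson gave 0.028 and 0.026, a rise of about 0.003 to 0.004.

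**The case against.** The strongest reply is that the loss needs three things the plan does not commit to: the fallback is triggered, Poisson is chosen, and default standard errors are used. Poisson is introduced only as an example, and no standard-error type is stated. With scaled or robust standard errors the loss all but disappears. This stands, and every figure above is conditional on it.

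A reader might infer three stronger things that the documents do not support.

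- *That the fallback would inflate type I error.* At both SDs derivable from the plan and means of 40 to 65, type I error is below 0.01. Inflation needs a mean below about 29 at SD 5.38, or a larger SD than the plan implies. At an assumed residual SD of 8, for instance, type I error would be 0.076 at mean 40 and 0.024 at mean 65. No section gives such an SD.
- *That the model will be chosen with knowledge of the treatment effect.* The plan does not say which data are examined. Baseline scores or a check pooled over arms would reveal little, and even the most favourable choice adds at most about 0.004.
- *That the effect in points would be lost.* A difference in points can be recovered from predicted means by arm. This is a reporting matter, though the plan does not address it.

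It is also fair to say that robust standard errors need not be compulsory, since the plan already has unequal arm variances in view. In a single-visit simulation with skewed residuals and active-to-TAU SD ratios of 0.7/1/1.4, arm-specific variances gave type I error of 0.0265/0.0245/0.0258, and robust standard errors gave 0.026/0.024/0.025.

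**Conclusion.** The point holds in limited form. The primary model depends on a normality judgement with no threshold, data source or timing, and the one fallback named does not suit a six-item score. If Poisson were used with default standard errors, the harm at the plan's own SD would be lost power, not false positives: from about 0.76 to between 0.62 and 0.34 at SD 5.38, and from about 0.88 to between 0.64 and 0.32 at SD 4.66. The SDs come from the plan's 2.8 points and d = 0.52; the means of 40 to 65 and the two-sided reading of alpha are assumptions. The linear model stayed near its nominal level with skewed residuals, so the switch buys little protection. It is worth removing because removal is cheap, not because the plan as written is bound to go wrong.

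**What to change.** In section 6.3.3, delete the fallback sentence and the normality condition. State that the primary HIT-6 comparison is the baseline-adjusted mean difference in points from the linear mixed model, whatever the observed distribution, with residual variance allowed to differ by arm (or with small-sample-corrected robust standard errors). List any generalized linear model as a sensitivity analysis, with dispersion-scaled or robust standard errors and the result given as a difference in points from predicted means by arm.

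The cost is a few sentences and no operational change. For the robust option, the power cost was simulated in a three-visit mixed model (assumed mean 60, SD 5.38, residual correlation 0.6, 10% missing at visit 1 and 25% at visit 3). It was 0.004 to 0.011 with equal variances. With the active-arm SD at 0.7 of TAU, power fell from 0.85 to 0.81 at visit 1 and from 0.80 to 0.75 at visit 3. In that case the pooled standard error had been too small (type I error 0.030 to 0.034), so part of the lost power was not genuine.

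### Holm instead of a fixed 0.025 for each HIT-6 comparison with TAU: a cheap gain in power to show that both therapies work, not the repair of an error

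*Combined protocol and SAP*

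**What the plan says.** Section 6.3.3 (Data analysis) defines the primary tests: "Two joint primary comparisons will be conducted comparing both active treatments to TAU". It then sets the multiplicity rule: "To adjust the alpha level for these joint hypotheses, we will interpret both at the alpha = 0.025 significance level". No stepwise procedure is mentioned. The overall alpha and the sidedness of the tests are not stated.

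The power paragraph in the same section uses the same level ("Assuming an alpha level of 0.025"), 64 participants per arm and a baseline-to-endpoint correlation of 0.50. It claims "power = 0.80 to detect an effect size of $d = 0.52$ between both of the joint primary comparisons". In scale units, "Our study is powered to detect an effect size of 2.8 points between groups" on the HIT-6, after adjustment for baseline. The same paragraph says that smaller changes are unlikely to matter clinically.

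Section 6.3.3 calls HIT-6 the primary outcome. Section 6.3.2 names both headache and PTSD symptoms as primary.

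**The concern.** With two hypotheses, Holm tests the smaller p-value at 0.025 and, if that is significant, the other at 0.05. It controls the familywise error at 0.05 under any dependence between the tests, and it rejects everything that the fixed rule rejects. The two rules differ only when one therapy has p at or below 0.025 and the other has p between 0.025 and 0.05. With p-values of 0.01 and 0.04, for example, the plan credits one therapy and Holm credits both.

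That case is relevant here. The Background expects both therapies to work through overlapping cognitive behavioral mechanisms, and the power statement is worded for both comparisons together. At stake is a second claim that the implied 0.05 budget would allow and the fixed rule withholds.

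**Working it through.** **Inputs from section 6.3.3.** 64 per arm; two comparisons that share the TAU arm; alpha 0.025 each; r = 0.50; d = 0.52; difference 2.8 points; stated power 0.80.

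**Assumptions, because the plan is silent.** Two-sided tests; overall alpha 0.05; common variance; no dropout; d in units of the unadjusted SD. With equal arms, the shared TAU arm gives a correlation of 0.5 between the two test statistics.

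**Step 1. Standard error and noncentrality.**
- Implied SD = 2.8 / 0.52 = 5.38.
- Residual SD factor = sqrt(1 − 0.50²) = 0.866.
- SE = 5.38 × 0.866 × sqrt(2/64) = 0.824 points.
- Noncentrality = 2.8 / 0.824 = 3.40.
- Critical values: 2.241 at 0.025 and 1.960 at 0.05.

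**Step 2. Reproduce the plan's 0.80.**
- One comparison at 0.025: Φ(3.397 − 2.241) = Φ(1.156) = 0.876.
- Both comparisons at 0.025: bivariate normal probability at (1.156, 1.156) with correlation 0.5 = 0.796. With t on 188 df it is 0.789.

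The stated 0.80 therefore reproduces as power to win both comparisons, not as baseline-adjusted power for one.

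**Step 3. Holm on the same inputs.** Holm adds the cases in which one statistic exceeds 2.241 and the other lies between 1.960 and 2.241. By symmetry each of the two orderings has probability 0.035.
- Both: 0.796 + 2 × 0.035 = 0.866.
- Each: 0.876 + 0.035 = 0.911.
- At least one: 2 × 0.876 − 0.796 = 0.956 under either rule, because Holm's first step is the fixed test.

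| Scenario | Quantity | Fixed 0.025 | Holm |
|---|---|---|---|
| Both d = 0.52 | both shown | 0.796 | 0.866 |
| Both d = 0.52 | each | 0.876 | 0.911 |
| Both d = 0.52 | at least one | 0.956 | 0.956 |
| Effects 2.8 and 2.0 points | weaker therapy | 0.574 | 0.666 |
| Only one works (t, 188 df) | the effective therapy | 0.871 | 0.873 |
| d = 0.52 with no gain from baseline | both shown | 0.632 | 0.731 |
| 48 per arm (25% loss, assumed) | both shown | 0.631 | 0.730 |

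As a yardstick, 0.80 for both is first passed at 65 per arm under the fixed rule (0.804) and at 56 under Holm (0.808).

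**Step 4. Error rates.**
- Neither therapy works: familywise error 0.0465 under both rules.
- One therapy has the 2.8-point effect and the other none: false-positive rate for the null therapy 0.025 fixed, about 0.044 Holm.
- One has a very large effect and the other none: 0.025 fixed, about 0.050 Holm.

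All stay within 0.05.

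**Step 5. What an added rejection looks like.** The second difference must lie between 1.960 × 0.824 = 1.62 and 2.241 × 0.824 = 1.85 points. Because its p-value exceeds 0.025, its 97.5% interval includes zero.

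**The case against.** The fixed rule is prespecified, valid and consistent with the power calculation. A reader might infer that it is a mistake, or that it leaves the trial short of power. The documents support neither: on the reading that reproduces 0.80, the plan meets its target under its own rule.

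A reader might also infer that Holm gives clearly more power at no cost. That goes too far in four ways.

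- **The gain is conditional.** It needs both therapies to have an effect. The chance of at least one success does not move, and if only one therapy works the gain is about 0.2 percentage points.
- **Error is spent.** The rate for a single true null rises from 0.025 towards 0.05. This is within the bound but is a real trade.
- **Intervals stop matching.** The fixed rule pairs naturally with 97.5% intervals. Under Holm the mismatch arises in exactly the cases that the change is meant to gain.
- **Relevance.** Added rejections come from observed differences of 1.62 to 1.85 points, below 2.8 and also below the 2.5 points that section 6.3.3 links to the smaller perceived improvement. The fixed rule itself rejects from 1.85 points upwards, so this calls for care in interpretation under either rule, but Holm adds to it.

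Two further points stand. Section 6.1.7 describes past travel barriers for participants in this study, so recruitment had begun, and a change to the success rule needs a documented date and reason. Section 6.3.2 names PTSD symptoms as a further primary outcome. A Holm pair for each of two outcomes would sum to 0.10, so the change must be tied to HIT-6 and does not settle that question.

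Step-down Dunnett might look interchangeable with Holm. It is not: it needs the correlation between the tests, and section 6.3.3 allows unequal variances, a non-normal fallback model and inverse probability weighting.

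**Conclusion.** The point holds as a cheap improvement, not as a defect. For the two HIT-6 comparisons, Holm keeps the familywise error within 0.05 and never loses a rejection. If both therapies have the planned effect, it adds about 7 percentage points to the power to show both (0.796 to 0.866) and about 3.5 to each comparison (0.876 to 0.911). It adds nothing to the chance of at least one success and next to nothing if one therapy is inert.

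The sizes rest on the assumptions listed in the check, chiefly two-sided tests, an overall alpha of 0.05 and full follow-up. The ordering of the two rules does not depend on those power inputs. The documents do not support calling the fixed split wrong, the trial underpowered because of it, or the alternative free of cost.

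**What to change.** Before unblinded analysis, and with the date and reason recorded, replace the alpha sentence in section 6.3.3 with:

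*The two primary HIT-6 comparisons with TAU will be tested with the Holm procedure at familywise two-sided alpha 0.05 (smaller p-value against 0.025; if significant, the other against 0.05).*

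Add three reporting rules:
- Give Holm-adjusted p-values: twice the smaller p-value, and for the other the larger of that figure and its own p-value, each capped at 1.
- Report 97.5% intervals as descriptive, noting that they include zero for a second-step rejection with p between 0.025 and 0.05.
- Interpret each estimated difference against the 2.8-point mark alongside the test.

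Do not offer step-down Dunnett as an option. The cost is a short text change, with no new participants, data or model. The plan should acknowledge the higher error rate for a single true null.
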